6.6.2.2.11. Immune-Related Cardiac Events

Immune-Related Myocarditis

Immune-related myocarditis has been associated with the administration of atezolizumab. Immune-related myocarditis should be suspected in any subject presenting with signs or symptoms suggestive of myocarditis, including, but not limited to, laboratory (eg, B-type natriuretic peptide) or cardiac imaging abnormalities, dyspnea, chest pain, palpitations, fatigue, decreased exercise tolerance, or syncope. Myocarditis may also be a clinical manifestation of myositis and should be managed accordingly. Immune-related myocarditis needs to be distinguished from myocarditis resulting from infection (commonly viral, eg, in a subject who reports a recent history of gastrointestinal illness), ischemic events, underlying arrhythmias, exacerbation of preexisting cardiac conditions, or progression of malignancy.

All patients with possible myocarditis should be urgently evaluated by performing cardiac enzyme assessment, an ECG, a chest X-ray, an echocardiogram, and a cardiac MRI as appropriate per institutional guidelines. A cardiologist should be consulted. An endomyocardial biopsy may be considered to enable a definitive diagnosis and appropriate treatment, if clinically indicated.

Patients with signs and symptoms of myocarditis, in the absence of an identified alternate etiology, should be treated according to the guidelines in [Table 25](#).

Immune-Mediated Pericardial Disorders

Immune-mediated pericarditis should be suspected in any patient presenting with chest pain and may be associated with immune-mediated myocarditis (see section on myocarditis above).

Immune-mediated pericardial effusion and cardiac tamponade should be suspected in any patient presenting with chest pain associated with dyspnea or hemodynamic instability.

Patients should be evaluated for other causes of pericardial disorders such as infection (commonly viral), cancer related (metastatic disease or chest radiotherapy), cardiac injury related (post myocardial infarction or iatrogenic), and autoimmune disorders, and should be managed accordingly.

All patients with suspected pericardial disorders should be urgently evaluated by performing an ECG, chest X-ray, transthoracic echocardiogram, and cardiac MRI as appropriate per institutional guidelines. A cardiologist should be consulted. Pericardiocentesis should be considered for diagnostic or therapeutic purposes, if clinically indicated.

Patients with signs and symptoms of pericarditis, pericardial effusion, or cardiac tamponade, in the absence of an identified alternate etiology, should be treated according to the guidelines in [Table 25](#). Withhold treatment with atezolizumab for Grade 1 pericarditis and conduct a detailed cardiac evaluation to determine the etiology and manage accordingly.

Table 25: Management Guidelines for Immune-Related Cardiac Events

Event	Management
Immune-related myocarditis, Grades 2-4	
• Permanently discontinue atezolizumab and contact the Sponsor.^a• Refer subject to cardiologist• Initiate treatment as per institutional guidelines and consider antiarrhythmic drugs, temporary pacemaker, ECMO, or VAD as appropriate.
Immune-related pericardial disorders, Grades 2-4	
• Initiate treatment with 1-2 mg/kg/day IV methylprednisolone or equivalent and convert to 1-2 mg/kg/day oral prednisone or equivalent upon improvement.• If event does not improve within 48 hours after initiating corticosteroids, consider adding an immunosuppressive agent.• If event resolves to Grade 1 or better, taper corticosteroids over \geq 1 month.

^a ECMO, extracorporeal membrane oxygenation; IV, intravenous; VAD, ventricular assist device.

Resumption of atezolizumab may be considered in subjects who are deriving benefit and have fully recovered from the immune-related event. The decision to rechallenge with atezolizumab should be based on investigator's assessment of benefit-risk, and documented by the investigator. The Medical Monitor is available to advise as needed.

6.6.2.12. Immune-Related Myositis

Myositis has been associated with the administration of atezolizumab. Myositis or inflammatory myopathies are a group of disorders sharing the common feature of inflammatory muscle injury; dermatomyositis and polymyositis are amongst the most common disorders. Initial diagnosis is based on clinical (muscle weakness, muscle pain, skin rash in dermatomyositis), biochemical (serum creatinine-kinase increase), and imaging (electromyography/MRI) features and is confirmed with a muscle biopsy.

Subjects with possible myositis should be referred to a rheumatologist or neurologist. Subjects with possible myositis should be monitored for signs of myocarditis.

Subjects with signs and symptoms of myositis, in the absence of an identified alternate etiology, should be treated according to the guidelines presented in [Table 26](#).

Table 26: Management Guidelines for Immune-Related Myositis

Event	Management
Immune-related myositis, Grade 1	
• Continue atezolizumab• Refer subject to rheumatologist or neurologist• Initiate treatment as per institutional guidelines

Event	Management
Immune-related myositis, Grade 2	
 Withhold atezolizumab for up to 12 weeks after event onset^a and contact Sponsor. Refer subject to rheumatologist or neurologist Initiate treatment as per institutional guidelines Consider treatment with corticosteroid equivalent to 1-2 mg/kg/day IV methylprednisolone and convert to 1-2 mg/kg/day oral prednisone or equivalent upon improvement. If corticosteroids are initiated and event does not improve within 48 hours after initiating corticosteroids, consider adding an immunosuppressive agent If event resolves to Grade 1 or better, resume atezolizumab.^b If event does not resolve to Grade 1 or better while withholding atezolizumab,
Immune-related myositis, Grade 3	
 Withhold atezolizumab for up to 12 weeks after event onset^a and contact the Sponsor Refer subject to rheumatologist or neurologist Initiate treatment as per institutional guidelines Respiratory support may be required in more severe cases Initiate treatment with corticosteroid equivalent to 1-2 mg/kg/day IV methylprednisolone or higher dose bolus if subject is severely compromised (eg, cardiac or respiratory symptoms, dysphagia, or weakness that severely limits mobility); convert to 1-2 mg/kg/day oral prednisone or equivalent upon improvement. If event does not improve within 48 hours after initiating corticosteroids, consider adding an immunosuppressive agent. If event resolves to Grade 1 or better, resume atezolizumab.^b If event does not resolve to Grade 1 or better while withholding atezolizumab, permanently discontinue atezolizumab and contact the Sponsor. Permanently discontinue atezolizumab and contact Medical Monitor.^c For recurrent events, treat as a Grade 4 event. Permanently discontinue atezolizumab and contact the Sponsor.
Immune-related myositis, Grade 4	
 Permanently discontinue atezolizumab and contact the Sponsor.^c Refer subject to rheumatologist or neurologist Initiate treatment as per institutional guidelines. Respiratory support may be required in more severe cases Initiate treatment with corticosteroid equivalent to 1-2 mg/kg/day IV methylprednisolone or higher dose bolus if subject is severely compromised (eg, cardiac or respiratory symptoms, dysphagia, or weakness that severely limits mobility); convert to 1-2 mg/kg/day oral prednisone or equivalent upon improvement. If event does not improve within 48 hours after initiating corticosteroids, consider adding an immunosuppressive agent. If event resolves to Grade 1 or better, taper corticosteroids over \geq 1 month.

Event	Management
IV, intravenous	
^a Atezolizumab may be withheld for a period of time (ie, > 12 weeks after event onset) to allow for corticosteroids (if initiated) to be reduced to ≤ 10 mg/day oral prednisone or equivalent. The acceptable length of the extended period of time must be based on an assessment of benefit-risk by the Investigator and in alignment with the protocol requirements for duration of treatment and documented by the investigator. The Medical Monitor is available to advise as needed.	
^b If corticosteroids have been initiated, they must be tapered over ≥ 1 month to ≤ 10 mg/day oral prednisone or equivalent before atezolizumab can be resumed.	
^c Resumption of atezolizumab may be considered in subjects who are deriving benefit and have fully recovered from the immune-related event. The decision to rechallenge subjects with atezolizumab should be based on Investigator's assessment of benefit-risk, and documented by the Investigator. The Medical Monitor is available to advise as needed.	

6.6.2.2.13. Hemophagocytic Lymphohistiocytosis and Macrophage Activation Syndrome

Immune-mediated reactions may involve any organ system and may lead to hemophagocytic lymphohistiocytosis (HLH) and macrophage activation syndrome (MAS).

Clinical and laboratory features of severe CRS overlap with HLH, and HLH should be considered when CRS presentation is atypical or prolonged.

Subjects with suspected HLH should be diagnosed according to published criteria by McClain and Eckstein (2014). A subject should be classified as having HLH if five of the following eight criteria are met:

- Fever $\geq 38.5^{\circ}\text{C}$
- Splenomegaly
- Peripheral blood cytopenia consisting of at least two of the following:
 - Hemoglobin < 90 g/L (9 g/dL) (< 100 g/L [10 g/dL] for infants < 4 weeks old)
 - Platelet count $< 100 \times 10^9/\text{L}$ (100,000/ μL)
 - ANC $< 1.0 \times 10^9/\text{L}$ (1000/ μL)
- Fasting triglycerides > 2.992 mmol/L (265 mg/dL) and/or fibrinogen < 1.5 g/L (150 mg/dL)
- Hemophagocytosis in bone marrow, spleen, lymph node, or liver
- Low or absent natural killer cell activity
- Ferritin > 500 mg/L (500 ng/mL)
- Soluble interleukin 2 (IL-2) receptor (soluble CD25) elevated ≥ 2 standard deviations above age-adjusted laboratory-specific norms

Subjects with suspected MAS should be diagnosed according to published criteria for systemic juvenile idiopathic arthritis by Ravelli et al (2016). A febrile subject should be classified as having MAS if the following criteria are met:

- Ferritin > 684 mg/L (684 ng/mL)
- At least two of the following:
 - Platelet count $\leq 181 \times 10^9/L$ (181,000/ μ L)
 - AST ≥ 48 U/L
 - Triglycerides > 1.761 mmol/L (156 mg/dL)
 - Fibrinogen ≤ 3.6 g/L (360 mg/dL)

Subjects with suspected HLH or MAS should be treated according to the guidelines in [Table 27](#).

Table 27: Management Guidelines for Suspected Hemophagocytic Lymphohistiocytosis or Macrophage Activation Syndrome

Event	Management
Suspected HLH or MAS	
 • Permanently discontinue atezolizumab and contact Medical Monitor. • Consider patient referral to hematologist. • Initiate supportive care, including intensive care monitoring if indicated per institutional guidelines. • Consider initiation of IV corticosteroids, an immunosuppressive agent, and/or anti-cytokine therapy. • If event does not respond to treatment within 24 hours, contact Sponsor and initiate treatment as appropriate according to published guidelines (La Rosée 2015; Schram and Berliner 2015; La Rosée et al 2019). • If event resolves to Grade 1 or better, taper corticosteroids over ≥ 1 month. • If event does not improve within 48 hours after initiating corticosteroids, consider adding an immunosuppressive agent.

HLH, hemophagocytic lymphohistiocytosis; IV, intravenous; MAS, macrophage activation syndrome

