irAE	
Events suggestive of hypersensitivity, infusion-related reactions, cytokine release syndrome, influenza-like illness, hemophagocytic lymphohistiocytosis, and macrophage activation syndrome
irAE	
Nephritis
irAE	
Ocular toxicities (eg, uveitis, retinitis)
irAE	
Myositis
irAE	
Myopathies, including rhabdomyolysis
irAE	
\geq Grade 2 cardiac disorders
irAE	
Vasculitis
irAE	
Severe cutaneous reactions (eg, Stevens-Johnson syndrome, bullous dermatitis, toxic epidermal necrolysis)

ALT, alanine aminotransferase; AST, aspartate aminotransferase; DILI, drug-induced liver injury; irAE, immune-related adverse event; ULN, upper limit of normal.

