Grade 2:^a Fever ^b with hypotension not requiring vasopressors and/or Hypoxia requiring low-flow oxygen ^d by nasal cannula or blow-by	
 • Immediately interrupt infusion. • Upon symptom resolution, wait for 30 minutes and then restart infusion at half the rate being given at the time of event onset. • If symptoms recur, discontinue infusion of this dose. • Administer symptomatic treatment.^c • For hypotension, administer IV fluid bolus as needed. • Monitor cardiopulmonary and other organ function closely (in the ICU, if appropriate). Administer IV fluids as clinically indicated, and manage constitutional symptoms and organ toxicities as per institutional practice. • Rule out other inflammatory conditions that can mimic CRS (eg, sepsis). If no improvement within 24 hours, initiate workup and assess for signs and symptoms of HLH or MAS. • Consider IV corticosteroids (eg, methylprednisolone 2 mg/kg/day or dexamethasone 10 mg every 6 hours). • Consider anti-cytokine therapy.^c • Consider hospitalization until complete resolution of symptoms. If no improvement within 24 hours, manage as per Grade 3, that is, hospitalize patient (monitoring in the ICU is recommended), permanently discontinue atezolizumab, and contact Sponsor. • If symptoms resolve to Grade 1 or better for 3 consecutive days, the next dose of atezolizumab may be administered. For subsequent infusions, consider administration of oral premedication with antihistamines, anti-pyretics, and/or analgesics and monitor closely for IRRs and/or CRS. • If symptoms do not resolve to Grade 1 or better for 3 consecutive days, contact Sponsor.

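### The ferritin cut-offs for HLH and MAS are each printed in two units that differ 1000-fold (mg/L against ng/mL)

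*Protocol*

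**What the plan says.** Section 6.6.2.2.13 of the protocol gives a criteria list for each condition and cites a publication for each.

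- **HLH:** "A subject should be classified as having HLH if five of the following eight criteria are met". One of the eight is "Ferritin > 500 mg/L (500 ng/mL".
- **MAS:** "A febrile subject should be classified as having MAS if the following criteria are met". The first criterion is "Ferritin > 684 mg/L (684 ng/mL". The second asks for at least two of four further items: platelets, AST, triglycerides and fibrinogen. Ferritin is therefore required, and the other four are alternatives.

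Three other places lead to these conditions or depend on them:

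- **Appendix G**, for Grade 2, 3 and 4 infusion-related reactions or cytokine release syndrome: "If no improvement within 24 hours, initiate workup and assess for signs and symptoms of HLH or MAS".
- **Table 27**, introduced by "Subjects with suspected HLH or MAS should be treated according to the guidelines in" that table. It calls for permanent discontinuation of atezolizumab.
- **Table 31** (Section 8.3), which lists both conditions as adverse events of special interest within the entry that begins "Events suggestive of hypersensitivity, infusion-related reactions, cytokine release syndrome".

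Neither the protocol nor the SAP restates or corrects the two ferritin cut-offs elsewhere.

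**The concern.** On each ferritin line the same numeral is attached to mg/L and to ng/mL, and these units differ by a factor of 1000. A site cannot satisfy both figures, and the mg/L figure is printed first.

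The lists say when a subject should be classified as having HLH or MAS, and Appendix G sends sites to assess for these conditions when a potentially serious reaction has not improved within 24 hours. For MAS, where ferritin is mandatory, applying the mg/L figure would in effect rule the classification out. For HLH it would remove one of eight items, leaving five needed from seven. Both statements assume that ferritin in the hundreds of mg/L is not reached in practice; the documents give no ferritin range.

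**Working it through.** **Inputs.** All values are from Protocol Section 6.6.2.2.13. The only outside figure is the triglyceride conversion, assumed to be 88.57 mg/dL per mmol/L.

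**Step 1: the ferritin lines.** 1 mg/L = 10^6 ng per 10^3 mL = 1000 ng/mL, and 1 ng/mL = 1 microgram/L.

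- HLH: 500 mg/L = 500 × 1000 = 500,000 ng/mL. Printed alongside: 500 ng/mL. Ratio 500,000 / 500 = 1000.
- MAS: 684 mg/L = 684 × 1000 = 684,000 ng/mL. Printed alongside: 684 ng/mL. Ratio 684,000 / 684 = 1000.
- In the other direction, 500 ng/mL = 500 micrograms/L = 0.5 mg/L, and 684 ng/mL = 684 micrograms/L = 0.684 mg/L.

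Neither printed equivalence can be reproduced.

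**Step 2: the other two-unit values in the section, as a control.**

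| Value | First unit | Second unit | Check | Agrees |
|---|---|---|---|---|
| Hemoglobin (HLH) | 90 g/L | 9 g/dL | 90/10 = 9 | yes |
| Hemoglobin, infants (HLH) | 100 g/L | 10 g/dL | 100/10 = 10 | yes |
| Platelets (HLH) | 100 × 10^9/L | 100,000/μL | 100 × 10^9/10^6 = 100,000 | yes |
| ANC (HLH) | 1.0 × 10^9/L | 1000/μL | 10^9/10^6 = 1000 | yes |
| Triglycerides (HLH) | 2.992 mmol/L | 265 mg/dL | 265/88.57 = 2.992 | yes |
| Fibrinogen (HLH) | 1.5 g/L | 150 mg/dL | 1.5 × 100 = 150 | yes |
| Ferritin (HLH) | 500 mg/L | 500 ng/mL | 500 × 1000 = 500,000 | **no** |
| Ferritin (MAS) | 684 mg/L | 684 ng/mL | 684 × 1000 = 684,000 | **no** |
| Platelets (MAS) | 181 × 10^9/L | 181,000/μL | 181 × 10^9/10^6 = 181,000 | yes |
| Triglycerides (MAS) | 1.761 mmol/L | 156 mg/dL | 156/88.57 = 1.761 | yes |
| Fibrinogen (MAS) | 3.6 g/L | 360 mg/dL | 3.6 × 100 = 360 | yes |

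Nine of 11 agree. The two that fail are both ferritin, both by exactly 1000 and both with identical numerals. With micrograms/L in place of mg/L, both would agree exactly.

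**Step 3: where the two readings give different answers.**

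- MAS: for any ferritin above 684 and up to 684,000 ng/mL, the mandatory item is met on the ng/mL figure and not met on the mg/L figure.
- HLH: the same holds above 500 and up to 500,000 ng/mL. If the item cannot be met, 8 − 1 = 7 items remain and five are still needed.

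**The case against.** The mismatch is hard to dispute; the argument is about its weight and its cause.

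**Little depends on the cut-offs.** Table 27 acts on suspicion. Appendix G asks for signs and symptoms and names no ferritin value. Table 31 covers events suggestive of these conditions, and SAP Section 8.3 builds special-interest events from preferred terms, not laboratory values. Ferritin is in neither the protocol's laboratory panel (Table 2) nor the SAP's list of abnormalities (Section 8.4.1). All of this stands, and it confines the point to the classification itself.

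**The text partly protects itself.** The ng/mL figure is beside each mg/L figure, the section refers readers to published criteria, and Table 27 brings in the Medical Monitor and suggests a hematology referral. An experienced clinician would probably notice the slip. This also stands, but it does not make the line correct.

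**A micro sign may have been lost when the PDF was converted to text.** That would produce identical numerals and a factor of exactly 1000 on both lines, and it cannot be fully excluded without the original page. It is unlikely, because the micro sign survives in the same two lists (/μL for platelets and ANC) and elsewhere in the protocol (μmol/L, μM). Those are not microgram units, so the evidence is strong but not conclusive.

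**Which unit is right depends on publications outside the documents.** True. The inconsistency does not depend on them; the choice of correction does.

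**Conclusion.** The point holds. As printed, both ferritin criteria are internally inconsistent by a factor of 1000, and they are the only 2 of the section's 11 two-unit values that are. The identical numerals suggest mg/L was written for micrograms/L, but the documents do not say which unit was intended.

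This is an incorrect decision threshold in the criteria for a serious immune toxicity, so it should be corrected, though its reach is small. No effect is claimed on treatment discontinuation, counts of special-interest events, efficacy endpoints, alpha or sample size. The arithmetic rests only on the definition of the units. The conclusion that the protocol itself is wrong also assumes that the converted text matches the original page.

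**What to change.** Look at the original page, then check both ferritin lines against the published criteria that Section 6.6.2.2.13 cites. Print units that denote the same quantity. If the ng/mL figures are confirmed, the cut-offs become:

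- HLH: ferritin above 500 micrograms/L (500 ng/mL), equal to 0.5 mg/L.
- MAS: ferritin above 684 micrograms/L (684 ng/mL), equal to 0.684 mg/L.

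Writing out micrograms avoids a repeat of the same slip. The change is two unit corrections, made by amendment or by a letter to investigators. It adds no tests and, if the ng/mL figures are the intended ones, leaves the criteria themselves unchanged.

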6.6.2.2.14. Other Atezolizumab-Associated Immune-Related Adverse Events

The following general management guidance should be applied for any other atezolizumab-associated irAEs:

- Grade 2 or 3: delay atezolizumab dosing up to 12 weeks until irAE recovers to Grade 0-1 and corticosteroids have been reduced to ≤ 10 mg prednisone or equivalent per day
- Grade 4 or recurrent Grade 3: permanently discontinue atezolizumab

6.6.2.2.15. Embryo-Fetal Toxicity

Based on its mechanism of action, atezolizumab can cause fetal harm when administered to a pregnant woman. Animal studies have demonstrated that inhibition of the PD-L1/PD-1 pathway can lead to increased risk of immune-related rejection of the developing fetus resulting in fetal death. If atezolizumab is used during pregnancy, or if the subject becomes pregnant while taking atezolizumab, advise the subject of the potential risk to a fetus. Advise females of reproductive potential to use effective contraception during treatment with atezolizumab and for at least 5 months after the last dose.

6.6.2.3. Sorafenib

The most common adverse reactions ($\geq 20\%$) for sorafenib are diarrhea, fatigue, infection, alopecia, hand-foot skin reaction, rash, weight loss, decreased appetite, nausea, GI and abdominal pains, hypertension, and hemorrhage.

Management of severe or intolerable adverse reactions may require temporary dose reduction and/or interruption of sorafenib therapy.

Temporary interruption of sorafenib is recommended in subjects undergoing major surgical procedures. Temporary interruption or permanent discontinuation of sorafenib may be required for the following:

- Cardiac ischemia or infarction
- Hemorrhage requiring medical intervention
- Severe or persistent hypertension despite adequate anti-hypertensive therapy
- GI perforation
- QTc prolongation
 - If at any time on study there is an increase in QTcF to an absolute value > 500 ms or > 60 ms above the baseline value, two additional ECGs must be performed with intervals not less than 3 min apart within 30 min after the initial ECG. If the average QTcF from the three ECGs is > 500 ms or > 60 ms above baseline, the following actions must be taken:
 - Discontinue treatment
 - Hospitalize symptomatic subjects (eg, with palpitations, dizziness, syncope, orthostatic hypotension) or those with a significant ventricular arrhythmia on ECG for a thorough cardiology evaluation and management

- Send copies of ECGs to central ECG laboratory for independent read
- Severe DILI

For additional details on warnings, precautions, possible AEs and management guidance of AEs refer to the most current local prescribing information appropriate to the respective study site location.

6.6.2.4. Management of Hepatobiliary Adverse Events

As this study will be evaluating subjects with advanced HCC, hepatobiliary AEs are expected to occur relatively frequently.

Elevations of aminotransferases and bilirubin have been observed during treatment with some anticancer therapies including cabozantinib, atezolizumab, and sorafenib. Modifications of study treatment may be appropriate to address these events, and management guidance for these agents in response to increases in aminotransferases and bilirubin is provided in this section.

General Guidance for Aminotransferase and Bilirubin Abnormalities

Patients with advanced liver cancer may have elevations of aminotransferases (ALT and AST) or bilirubin due to their disease. As such, subjects on this study may enroll with elevations of AST/ALT up to 5 \times ULN at baseline. It is recommended that subjects with elevations of ALT, AST, and/or bilirubin have more frequent laboratory monitoring of these parameters.

Evaluation of subjects with elevated transaminases or total bilirubin should be individualized and guided by the presence of specific risk factors such as illnesses which affect liver function (eg, infectious and non-infectious causes of hepatitis, liver cirrhosis, thrombosis of portal or hepatic vein), concomitant hepatotoxic medication, alcohol consumption, and cancer related causes. If possible, hepatotoxic concomitant medications should be discontinued in subjects who develop increased values of ALT, AST, or bilirubin. For patients with elevated LFTs, concurrent medication, viral hepatitis, and toxic or neoplastic etiologies should be considered and addressed, as appropriate.

Subjects with right upper-quadrant abdominal pain and/or unexplained nausea or vomiting should have liver function tests (LFTs) performed immediately and reviewed before administration of the next dose of study drug.

Guidance for Management of Hepatotoxicity

Guidance is provided on management of hepatotoxicity related to atezolizumab in [Table 28](#) and to cabozantinib in [Table 29](#).

Table 28: Management Guidelines for Hepatic Events Associated with Atezolizumab

Severity of Event	Management
If AST/ALT is within normal limits at baseline and increases to $> 3 \times$ ULN to $\leq 10 \times$ ULN or	All events: 
 Monitor LFTs more frequently until return to baseline values. Withhold atezolizumab for up to 12 weeks after event onset.^a For events of > 5 days' duration, consider initiating treatment with 1-2 mg/kg/day prednisone or equivalent.
If AST/ALT is $>$ ULN to $\leq 3 \times$ ULN at baseline and increases to $> 5 \times$ ULN to $\leq 10 \times$ ULN or	
 If event resolves to baseline or to Grade 1 or better, resume atezolizumab.^b If event does not resolve to baseline or to Grade 1 or better while withholding atezolizumab, permanently discontinue atezolizumab and contact the Sponsor.^c
If AST/ALT is $> 3 \times$ ULN to $\leq 5 \times$ ULN at baseline and increases to $> 8 \times$ ULN to $\leq 10 \times$ ULN	
If AST or ALT increases to $> 10 \times$ ULN or total bilirubin increases to $> 3 \times$ ULN	
 Permanently discontinue atezolizumab and contact the Sponsor.^c Consider subject referral to GI specialist for evaluation and liver biopsy to establish etiology of hepatic injury. Initiate treatment with 1-2 mg/kg/day prednisone or equivalent. If event does not improve within 48 h after initiating corticosteroids, consider adding an immunosuppressive agent. If event resolves to baseline, taper corticosteroids over ≥ 1 month.

ALT, alanine aminotransferase; AST, aspartate aminotransferase; GI, gastrointestinal; LFT, liver function test; ULN, upper limit of normal.

^a Atezolizumab may be withheld for a longer period of time (ie, > 12 weeks after event onset) to allow for corticosteroids (if initiated) to be reduced to ≤ 10 mg/day oral prednisone or equivalent. The acceptable length of the extended period of time must be based on the investigator's benefit-risk assessment and in alignment with the protocol requirements for the duration of treatment and documented by the investigator. The Medical Monitor is available to advise as needed.

^b If corticosteroids have been initiated, they must be tapered over ≥ 1 month to ≤ 10 mg/day oral prednisone or equivalent before atezolizumab can be resumed.

^c Resumption of atezolizumab may be considered in subjects who are deriving benefit and have fully recovered from the immune-related event. The decision to rechallenge subjects with atezolizumab should be based on the investigator's benefit-risk assessment and documented by the investigator. The Medical Monitor is available to advise as needed.

Table 29: Management Guidelines for Hepatic Events Associated with Cabozantinib

Severity of Event	Management
If ALT/AST is $\leq 3.0 \times$ ULN at baseline and increases to $\geq 5.0 \times$ ULN	
Interrupt cabozantinibMonitor LFTs more frequently until return to baseline valuesIf event resolves to baseline, or values stabilize at clinically acceptable levels, cabozantinib may be resumed at a reduced doseDiscontinue cabozantinib if hepatic dysfunction is not reversible despite temporary interruption of cabozantinib or drug-related ALT or AST $> 3 \times$ ULN in combination with total bilirubin $> 2 \times$ ULN without reasonable other explanation, consistent with DILI
If ALT/AST is $> 3.0 \times$ ULN to $\leq 5.0 \times$ ULN at baseline and doubles compared with the baseline values OR If ALT/AST is $> 3.0 \times$ ULN to $\leq 5.0 \times$ ULN at baseline and increases are less than double but are accompanied by progressive elevations of total bilirubin and/or elevations of coagulation tests (eg, INR).	
Interrupt cabozantinibMonitor LFTs more frequently until return to baseline values.If event resolves to baseline, or values stabilize at clinically acceptable levels, cabozantinib may be resumed at a reduced doseDiscontinue cabozantinib if hepatic dysfunction is not reversible despite temporary interruption of cabozantinib or drug-related ALT or AST $> 3 \times$ ULN in combination with total bilirubin $> 2 \times$ ULN without reasonable other explanation, consistent with DILI

ALT, alanine aminotransferase; AST, aspartate aminotransferase; DILI, drug-induced liver injury; INR, international normalized ratio; LFT, liver function test; ULN, upper limit of normal.

Hepatic Encephalopathy

Hepatic encephalopathy (HE) is a brain dysfunction caused by liver insufficiency. Hepatic encephalopathy is not uncommon in HCC patients and can be due to acute liver failure, portal systemic shunting and cirrhosis (Wong et al 2011, Willson et al 2013).

The clinical manifestations of HE include a wide spectrum of neurological or psychiatric abnormalities ranging from subclinical alterations to coma (Vilstrup et al 2014). As HE progresses, personality changes, such as apathy, irritability, and dis-inhibition may be observed. In the most severe form of HE, affected individuals may develop marked confusion or disorientation, amnesia, greatly dulled or reduced consciousness (stupor), or loss of consciousness (coma).

In the Sponsor-conducted CELESTIAL XL184-309 study, there was a higher incidence of hepatic encephalopathy and encephalopathy in the cabozantinib arm as compared to the placebo arm, and the median time to onset in the cabozantinib arm was 5.9 weeks. Cabozantinib has been associated with diarrhoea, vomiting, decreased appetite, and electrolyte abnormalities. In HCC patients with compromised livers, these non-hepatic effects may be precipitating factors for the development of hepatic encephalopathy. Additionally, a higher relative proportion of patients with moderate hepatic impairment (Child-Pugh B) developed hepatic encephalopathy with cabozantinib treatment. Furthermore, no cases of hepatic encephalopathy were reported in the RCC studies (METEOR and CABOSUN).

There is no specific test used to diagnose HE. The diagnosis of HE is usually based on a combination of medical history, symptoms, and a clinical exam. Blood tests (eg, ammonia levels) can identify abnormalities associated with liver, kidney, and other conditions that may contribute to HE. High blood-ammonia levels alone are not confirmatory or prognostic. However, if a subject's ammonia is normal, HE is less likely.

Patients with liver insufficiency and altered mental status should be evaluated for alternative causes of brain dysfunction, including irAEs. Rare cases (0.4% of patients) of meningoencephalitis have been observed in patients who received atezolizumab monotherapy (see the atezolizumab IB for more information). Additionally, the existence of precipitating factors for HE (diarrhea, vomiting, decreased appetite, infections, electrolyte abnormalities, gastrointestinal [GI] bleeding, diuretic overdose, and constipation) may aid in the diagnosis (Vilstrup et al 2014).

Adverse events of encephalopathy as graded per CTCAE v5.0 are shown below:

- Grade 1: Mild symptoms
- Grade 2: Moderate symptoms; limiting instrumental activities of daily living
- Grade 3: Severe symptoms; limiting self-care activities of daily living
- Grade 4: Life-threatening consequences; urgent intervention indicated
- Grade 5: Death

Management of Hepatic Encephalopathy

In patients with HE, the first step in management is to identify and treat the precipitating factors for HE including, but not limited to, diarrhea, vomiting, decreased appetite, electrolyte abnormalities, infections, GI bleeding, diuretic overdose, and constipation.

The following treatments are recommended (Vilstrup et al 2014):

- For symptomatic patients, consider treating with lactulose.
- After the initial episode, lactulose is recommended for prevention of recurrent episodes of HE.
- After the second episode, rifaximin is recommended as an add-on to lactulose for prevention of recurrent episodes of HE.
- Intravenous (IV) L-ornithine L-aspartate (LOLA) and branched-chain amino acids (BCAAs) can be used as an alternative or additional agent to treat patients nonresponsive to conventional therapy.
- Neomycin and metronidazole are alternative choices for treatment.

For patients with higher grades (\geq Grade 3) HE, consider hospitalization. Patients who are at risk or unable to protect their airway need more intensive monitoring and are ideally managed in an intensive care setting. Please refer to Vilstrup et al 2014 for further information. Detailed guidelines for the management of HE are provided in [Table 30](#).

Table 30: Management of Hepatic Encephalopathy Associated with Study Treatment

Hepatic Encephalopathy	
CTCAE v5.0 Grade	Recommended Guidelines for Management and Dose Modification
Grade 1	
Identify and treat any precipitating factor.
 
If symptomatic, consider treatment for AEs.
 
Continue study treatment if asymptomatic and an AE is manageable and tolerable.

Grade 2	
Consider treatment for AEs.
 
Continue study treatment if an AE is manageable and tolerable or interrupt study treatment for grade 2 AEs that are intolerable or cannot be adequately managed.
 
If an irAE is suspected, consider initiating steroid treatment.

Grade 3	
Consider hospitalization.
 
If an irAE is suspected, consider initiating steroid treatment.
 
Interrupt study treatment; Sponsor must be contacted to discuss treatment continuation upon resolution of AEs.
 
Study treatment may resume if the toxicity can be easily managed with a dose reduction and optimal medical care.

Grade 4	
Discontinue study treatment.
 
Consider hospitalization.
 
If an irAE is suspected, consider initiating steroid treatment.

AE, adverse event; CTCAE, Common Terminology Criteria for Adverse Events; HE, hepatic encephalopathy; irAE, immune-related adverse event.

Hepatic Failure

Hepatic failure is a disorder characterized by liver dysfunction. Hepatic failure can be severe and life-threatening. Hepatic failure may develop rapidly over days or weeks (acute) or gradually over months or years (chronic). Hepatic failure can also develop in the setting of HCC when the functional reserve of the hepatocytes has declined. Clinical findings potentially indicating hepatic failure include, but are not limited to: jaundice, portal hypertension, ascites, HE, GI bleeding, and kidney failure. Laboratory findings include abnormal plasma levels of ammonia, bilirubin, lactic dehydrogenase, alkaline phosphatase, aminotransferase, and/or prolongation of prothrombin time (ie, International Normalized Ratio [INR]).

Acute hepatic failure should be treated urgently as symptoms can worsen quickly. Subjects with acute hepatic failure may need to be treated in an intensive care setting.

Adverse events of hepatic failure are graded per CTCAE v5.0 as below:

- Grade 3: Asterixis; mild encephalopathy; DILI; limiting self-care (activities of daily living)
- Grade 4: Life-threatening consequences; moderate to severe encephalopathy; coma
- Grade 5: Death

For management of hepatic failure related encephalopathy and aminotransferase and bilirubin abnormalities (including DILI), refer to the guidance described above in this section. For Grade 4 events of hepatic failure, discontinue study treatment and treat symptoms accordingly.

